## Plans to give access to the full protocol, participant level-data and statistical code (31c)

To increase transparency and dissemination, all statistical code and fully anonymized dataset will be shared to an open-access repository (such as YODA, Zenodo, or Figshare) with a digital objective identifier once all planned publications are accepted or published as pre-print. Publication-specific datasets will potentially be posted along with published manuscripts in line with journal policies. If full anonymity cannot be achieved by removing unique data and identifies, a synthetic dataset will be created, which will mimic the original dataset by preserving the statistical properties and the relationships between variables. Specific funding for Open-Access publication fees will be sought to allow dissemination to clinicians lacking institutional access or funding for journal access.

[figure not shown]
## Effect moderation and mediation

As secondary analyses, we will perform moderation and mediation (if a superior treatment response in arm A is observed) analyses, which will be conducted and reported in accordance with the AGReMA Statement. Through mediation analysis, the total effect of exposure to treatment groups 1 vs A (i.e. between-group difference) on the outcome, will be parsed into indirect effect pathways from exposure to mediator, and from mediator to the primary outcome (KOOS child 'Sport/play' subscale), which are the effects of interest in this mediation analysis (figure 4). This will allow inference about the underlying responsible mechanisms for a potential effect. Such knowledge is key when optimizing or developing treatments, and for implementation efforts. As the sample size is not planned specifically for mediation analysis, these analyses are considered secondary and should be interpreted with caution mainly based on its effect size and precision. Although potential limitations of suboptimal power, this mediation analysis provides a novel preliminary step for potential identification of causal mechanisms for improvement in Osgood-Schlatter patients.

Mediators are represented by variables measured after randomization and before collection of outcome data, which are thought or known to be influenced by the treatment allocated to participants. As large-scale randomization balances known and unknown confounders that can potentially influence the outcome as well as the exposure-mediator pathway, randomized trials are the optimal setting to perform causal mediation analysis.

The assumed cauasal model we are investigating is illustrated as a directed acyclic graph below (figure 5) using the Dagitty software.

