# Secondary aims

- Compare secondary and exploratory patient-reported, clinical and objective measures of improvement and adverse effect, also at secondary timepoints at 3 months, and at long-term followup after 8, 10, 12, 24, and 48 months (table 10 & 11).
- Supply detailed trajectories of treatment response by collecting weekly self-reported measures and data from activity sensors during the entire 5 month core study period using visualizations and mixed effect analysis models.
- Explore factors associated with effect moderation or mediation to determine who will potentially benefit more or less of treatment, and the pontential mechanisms responsible.
- Investigate the experience of undergoing the intervention and identify potential barriers or facilitators to treatment and adherence.
- Evaluate features and procedures of the trial in a pilot-setting to assess operational feasibility

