## Sample size considerations {14}

The properties of the primary outcome measure KOOS-child and the "Sport/rec" subscale have been well investigated, with a validation study including adolescent participants with Osgood-Schlatter amongst other overuse- and acute knee disorders. A small cohort of patients in our clinic (n=16) who 1) were eligible for inclusion in the trial at baseline, 2) received the intervention in question and 3) attended follow-up, reported their global rating of improvement on a 7 point Likert scale ranging from 'much worse (7)' to 'much better (1)'. Patients who reported 'much better (1)' or 'better (2)' had a mean improvement on KOOS-child

'Sport/play' subscale of 12.7±16 points, whereas patients reporting less improvement ('little' improvement or 'no change') only had a 3.57 point increase. In absence of more robust specific data in terms of severity, intervention, and length of follow-up, we will utilize this 9 point difference as a threshold for determining superiority. We consider this to be a meaningful change and a relevant between-group difference, and is within the recommended range of 8-10 points (heartbeat-med.com/resources/knee-injury-and- osteoarthritis-outcome-score-koos). This change also exceeds the smallest detectable group-level change (2.66 points) and the standard error of measurement (8.02 points).

In order to detect such a change with a standard deviation of 16 points an  $\alpha$  level (type I/false positive error rate) of 5% and power ( $\beta$ -1, or probability of avoiding type II/false negative error rate) of 90%, 55 (54.8) participants per group would be needed based on an independent one-sided t-test (R 4.0.2, Foundation for Statistical Computing, Vienna, Austria; RStudio 1.0.153, power.t.test package). To account for a potential 15% dropout rate a total of 130 participants will be included.

This will correspond to a 0.56 Cohens d 'medium' effect size at 90% power (figure 3). The smallest effect size reliably detectable will thus be >0.482 (Cohens d 'small' effect size) at  $\geq$ 80% power (Jamovi 1.2.25, jpower module), surpassing the trivial (<0.2) and small (>0.2) effect size thresholds. We also consider this sample size to be operationally feasible within the given timeframe and with the resources available to our group.

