### Superiority framework and controlling error rates

The analysis will be evaluated based on a one-sided hypothesis as the trial employs a superiority design, meaning that if a one-sided test of significance fails in the direction of the experimental group, the null-hypothesis is rejected for our sample, and the level of significance in opposite direction is therefore not of interest. To further safeguard this choice, we have made the decision to obtain 90% power (up to 94.6% if all participants retained), corresponding to a 10% false negative error rate). By default, we will not perform adjustments for multiple comparisons as we have arranged our hypotheses in a prioritized order, and we will also conduct and report hypotheses testing in this pre-specified order. We will however adjust for multiple comparisons using Bonferroni corrections when multiple tests are performed for outcomes within the same construct or objective (e.g. the effect of group on acute pain response during loading, measured through 2 different outcomes: pain [0-10 NPRS] during maximal isometric knee extension test, and pain [0-10 NPRS] evoked from the Anterior Knee Pain Provocation test).

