### Statistical approach to mediation analysis

Mediation analysis will be based on interventional effects, this will allow for the inclusion of multiple mediators and account for dependence between mediators. With estimation done by Monte-Carlo based regressionmodels.Covariates will be included as moderators in the full model. For each mediator, we will calculate and report effect size as odds ratios and p-values, as well as 95% confidence intervals We will calculate and report estimated effect and percentage contribution to total effect for each mediator variable included in the final model, based of the mean indirect effect. The model will only include mediators that fulfill the temporal sequence of a causal relationship, that is exposure, mediator, outcome.

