## Dissemination plans {31a}

All members of the study group will be invited as co-authors on the specific publications according to the International Committee of Medical Journal Editors (ICMJE) recommendations and The Danish Code of Conduct for Research Integrity codec. All findings and results are planned to be published in international peer-reviewed scientific journals. Furthermore, the results will be presented at national and international conferences; as part of our collaborations with the Danish Society of Sports Physical Therapy, Danish Sports Medicine Association, Clinical-Academic Groups (CAGs) across Copenhagen University and University Hospitals; and as our capacity as IOC Research Center. The results will be posted to ClinicalTrials.gov once the primary results have been published. In addition, we will utilize appropriate social media channels to increase dissemination. The results will be published regardless of positive, negative, or inconclusive findings. [name] and [name] will enforce publications as first and senior authors respectively, unless other publication-specific contributions warrants or are otherwise agreed upon by the study group. We will frame the main conlusion based on the potentiel primary endpoint between-group difference, in line with the superiority framework, which will take into account the MCID (9 points), width of the confidence interval, the overlap of the confidence interval, and the statistical significance.

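### Mediation is run only if an undefined superiority condition is met, so the mechanism aim, which carries no condition, may go unanswered

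*Combined protocol and SAP*

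**What the plan says.** The section Effect moderation and mediation states: "we will perform moderation and mediation (if a superior treatment response in arm A is observed) analyses". As the sentence is built, the bracketed condition applies to mediation; moderation is not gated. No p-value, confidence limit or point difference is attached to the condition, and nothing is said about what happens if it is not met.

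Elsewhere the document describes superiority in three ways:

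- Superiority framework and controlling error rates: a one-sided test ("The analysis will be evaluated based on a one-sided hypothesis as the trial employs a superiority design").
- Sample size considerations: a point threshold ("we will utilize this 9 point difference as a threshold for determining superiority").
- Dissemination plans: a composite judgement for the main conclusion, which will "take into account the MCID (9 points), width of the confidence interval" as well as interval overlap and significance.

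The mechanism aim under Secondary aims is stated without any condition: "Explore factors associated with effect moderation or mediation to determine who will potentially benefit more or less of treatment", continuing to the mechanisms responsible. The section on additional analyses also lists mediation without a condition.

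Statistical approach to mediation analysis plans effect sizes per mediator as odds ratios with p-values and 95% confidence intervals, and also the "estimated effect and percentage contribution to total effect for each mediator variable included in the final model".

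**The concern.** A mediation analysis breaks a total effect into pathways. Each indirect effect is the product of treatment's effect on the mediator and the mediator's effect on the outcome. It can be non-zero when the total is small, and it can be estimated whatever the total turns out to be. Table 12 picks mediators that track separate parts of the treatment: pain and pressure sensitivity at week 4 for the sports break, controlled return at week 5 and flares at week 13 for graded exposure, and strength at week 13 for the exercises. If the overall result is modest or null, knowing which of these moved and which did not is useful for revising the treatment, and that is when the gate may withhold the analysis.

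Two further problems follow. Because the trigger is undefined, whether to run the analysis can be settled after the primary result is known. And if the trigger is significance, the percentages are calculated only in trials whose total effect has been selected for being large.

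**Working it through.** **Inputs.** From Sample size considerations: difference 9 points, SD 16, one-sided alpha 5%, power 90%, 55 (54.8) per group, 15% dropout, 130 in total. From Superiority framework and controlling error rates: 94.6% power if everyone is retained.

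**Reproducing the plan.** The exact two-sample t calculation gives 54.82 per group, and 110/0.85 = 129.4, rounded up to 130. Power at 65 per group comes to 93.9%, close to the stated 94.6%.

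**Chance that mediation is run, significance reading.** SE = 16 × √(2/n), and the critical difference is t(0.95, 2n − 2) × SE.

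- n = 55: SE = 3.05, critical difference 1.659 × 3.05 = 5.06 points.
- n = 65: SE = 2.81, critical difference 1.657 × 2.81 = 4.65 points.

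| True effect (points) | 9 | 6 | 4.5 | 3 | 0 |
|---|---|---|---|---|---|
| Run, 55 per arm | 90% | 62% | 43% | 25% | 5% |
| Run, 65 per arm | 94% | 68% | 48% | 28% | 5% |

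**Other readings, 65 per arm.** Direction only: Φ(D/SE). Observed difference of at least 9: 1 − Φ((9 − D)/SE). At D = 4.5, D/SE = 4.5/2.81 = 1.60, and (9 − 4.5)/SE is also 1.60, giving 95% and 5%.

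| Trigger | True 9 | True 4.5 | True 3 |
|---|---|---|---|
| Estimate above 0 | 99.9% | 95% | 86% |
| One-sided p<0.05 | 94% | 48% | 28% |
| Estimate at least 9 | 50% | 5% | 2% |

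**Inflation of the total when the significance gate opens, 65 per arm.** Mean given selection = D + SE × φ(z)/(1 − Φ(z)), with z = (4.65 − D)/SE. This gives 9.36 at a true 9 (1.04-fold), 7.46 at 6 (1.24-fold), 6.84 at 4.5 (1.52-fold) and 6.38 at 3 (2.13-fold).

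**What this does to the percentages.** The indirect effect is part of the total and is selected with it. In a single-mediator linear model, cov(indirect, total)/var(total) equals R², the share of within-arm outcome variance that the mediator explains. For an estimated total T and a true share PM, the expected share is therefore about [PM × D + R² × (T − D)]/T, so selection pulls the share towards R². At D = 4.5 and T = 6.84, with PM 50% and R² 0.1, this is (2.25 + 0.23)/6.84 = 36%.

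Simulated medians at a true 4.5 points, 65 per arm, significance gate. PM and R² are assumed, because the documents give neither:

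| True share | R² | Median, gated | Median, all trials |
|---|---|---|---|
| 50% | 0.1 | 35.5% | 45.1% |
| 50% | 0.5 | 49.7% | 49.7% |
| 30% | 0.5 | 36.4% | 32.2% |
| 20% | 0.7 | 36.6% | 25.2% |

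At a true 9 points under the same gate, the median stays within about 2 percentage points of the truth for true shares of 20% to 50% and R² of 0.1 to 0.7. That does not carry over to a 9-point gate: with a true share of 20% and R² 0.7, the gated median is 29.7%.

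**The case against.** Explaining an effect only once one has been seen is a legitimate, prespecified way to limit exploratory reporting in a trial that was not sized for mediation. The plan already calls the analysis secondary and preliminary, warns about power, and asks for interpretation by effect size and precision. It already reports an estimated effect and confidence intervals next to the percentage. Moderation is unaffected. All of this stands and limits the seriousness of the point. It does not supply a definition of the trigger or a fallback, and the caution concerns power, not selection.

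Three stronger readings are tempting, and the documents do not support them.

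- A reader might infer that the condition means statistical significance. The text says only that superiority is observed. If direction alone suffices, mediation would run in 95% of trials at a true 4.5 points and 86% at 3 (65 per arm).
- A reader might infer that the reported percentages are biased low because they are divided by an inflated total. That treats the numerator as fixed. The direction depends on whether R² lies below or above the true share. Some of any shortfall is also present with no gate: with a true 50% and R² 0.1, the ungated median is already 45.1%.
- A reader might infer that the arm A components work against each other and cancel. The plan presents the sports break as making graded exposure more successful, which is the same direction. Opposing pathways remain a hypothesis.

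**Conclusion.** The point holds as a minor one. The trigger is undefined, there is no fallback, and the mechanism aim has no matching condition. Under a one-sided 5% reading, a true effect of 3 to 6 points leaves mediation unrun in about 31% to 72% of trials with 65 per arm, or 38% to 75% with 55. Across the three readings at a true 4.5 points, the chance of running it spans 95% to 5%. These figures rest on the plan's SD of 16 and an unadjusted comparison of the groups.

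A significance gate conditions the percentages on a total inflated about 1.2-fold at 6 points and 1.5-fold at 4.5. The resulting bias has no fixed direction and is small at the design effect. Its size elsewhere rests on assumed shares and R² in a single-mediator model, whereas the plan fits several mediators together. No primary, secondary or safety between-group comparison is affected.

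**What to change.** In Effect moderation and mediation, delete the bracketed condition and state that mediation is run whatever the primary result and labelled exploratory.

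In Statistical approach to mediation analysis, make each indirect effect in KOOS-child points, with its 95% confidence interval, the main result in place of odds ratios, which do not suit an indirect effect on a 0–100 score. Give percentage contributions only as secondary figures, with an interval, and only when the total effect is clearly non-zero.

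If the sponsor prefers to keep a gate, the minimum is to define it before unblinding and to state the selection caveat beside the percentages.

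The cost is SAP wording. The mediators are scheduled for collection whatever the result, and the same code is run. The downside is one more exploratory analysis to report cautiously after a non-significant primary result.

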## Assumptions for causal mediation analysis

The four assumptions for unconfounded analysis of parsed mediation pathways require 1) no unmeasured exposure-outcome confounders, 2) no unmeasured mediator-outcome confounders, 3) no unmeasured exposure-mediator confounders, 4) no mediator-outcome confounder affected by exposure. Assumption 1 and 3 should be mitigated by randomization and potential covariate adjustment. Because mediators are not randomized it is possible for the mediator-outcome pathway to be confounded (assumption 2 and 4). To address assumption 2, we will include pre-treatment confounders based on available evidence and clinical expertise. This includes potential covariates/moderator variables outline (table 12) and baseline levels of the mediator-variables. Assumption 4 will be addressed by using interventional effects in the mediation analysis along with inclusion of confounders. In addition, to address the assumption of no positivity, that is, a zero risk of any participant exhibiting a positive characteristic of a mediation variable at baseline, all mediator variables with this potential issue, will be change-scores calculated from baseline.

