## Statistical methods

## Statistical methods for primary and secondary outcomes (20a)

Analyses will be performed by a statistician blinded to group allocation and will be performed using (R Foundation for Statistical Computing, Vienna, Austria) in the Rstudio interface (RStudio Team, Boston, USA).

Change scores for KOOS-child 'sport/play' score ( $\triangle$ KOOS) from baseline to month 5 will be calculated for all participants. We will fit a linear regression model using the 'lm' function for  $\triangle$ KOOS-child as the dependent variable and including group allocation as an independent variable. Covariates are described with their measurement, timing and justification in table 12, and will potentially be added to the model.82(p9),215 In order to not introduce unnecessary bias in the model, covariates will however only be included if doing so changes the primary estimate meaningfully, as we expect a equal distribution of these pre-specified covariates given the sample size. Significance level will not determine the inclusion of covariates. The linear model will be evaluated for linearity, multicollinearity, homogeneity of variance, distortion of outliers, homoskedasticity, correlation of variables, distribution of residuals using histograms. If these model assumptions are not met non parametric bootstrap estimation and tests will be used instead. Below we have outlined the intended steps with reproducible R code for Rstudio (version 3.6, 2021.09.0+351)

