## Number of predictors for mediations analysis

Based on our sample size of n=130 and the use of multiple regression models, power of >80% and alpha level of 5% (t = 1.658, Df = 109), we calculated the potential number of predictors as 16 based on Fritz & MacKinnon sample size recommendations for mediation analysis (G\*power 3.1.9.7, Düsseldorf University, Germany). In our current model, we have included 15 predictors (8 mediators and 7 potential covariates/moderators).

Variables	Measurement	Justification
Potential moderators/c	ovariates	
Growth velocity w0	Offset from predicted age at peak height velocity in years, calculated from clinically measured anthropometrics: sitting height, bodyweight, total stature, biological age.  Participants will be categorized into pre- (<-1.0 years offset), circa- (-1.0 to +0.5 years offset), and post-PHV (>+0.5 years offset), corrected for timing of the primary endpoint, resulting in a 5 month subtraction.	Overuse knee injuries, as well as injuries to the growth plate, in sports active adolescents are higher during peak height velocity and the year leading up to this point,  which is thought to be primarily due to vulnerable growth-related conditions, such as Osgood-Schlatter.  This has been supported by data showing higher growth velocity for Osgood-Schlatter patients than controls. 
Growth timing w0	Based on algorithms for calculating anticipated age of peak height velocity which incorporates data on parents adult stature, we will classify participants as early maturers, average maturers, and late maturers (girls: <10.94, 10.94-12.94, and >12.94 years, respectively; boys: <12.64, 12.64-14.64, and >14.64 years, respectively). 	Reaching skeletal maturity either late or on average is a risk factor for developing Osgood-Schlatter compared to early maturation. 
Fear of movement w13	Fear of movement will be captured by participants filling in the 17 items Tampa Scale of Kinesiophobia, each item scored on a 4-point likert scale with a score ranging from 0 to 68. 	Avoidance behavior might be related to a too apprehensive approach to gradual exposure and exercise therapy resulting in the patient not achieving a higher degree of participation in sports and physical activity. Osgood-Schlatter patients exhibits a high degree of kinesiophobia. 

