Pain during maximal knee loading w13	Participants will rate their pain using NRPS 0-10 during strength testing, that is, a 5 second maximal voluntary isometric contraction of the knee extensor muscles at 60° knee flexion.	Pain during loading is a key symptom of Osgood-Schlatter and is related to self-reported measures of quality of life, satisfaction with sports participation and hyperemia in the tendon.  The intervention aims to improve capacity to loading activities and should thus be better tolerated at this timepoint.					
Knee extension strength w13	Knee extension strength will be measured in newtons by handheld dynamometry during a 5 second maximal voluntary isometric contraction at 60° knee flexion. Newtons will be normalized to lever-length and bodyweight and expressed as Nm/kg.	Knee pain is known to reduce muscle function,  and strength training contribute to alleviate these deficits. 					
Distal patella tendon hyperemia w13	Rated by sonographers ad modum Öhberg from 'no neovessels' to '5 or more neovessels' on a 1-4 scale. 	A series of Osgood-Schlatter patients has been described for whom less hyperemia on color doppler ultrasound was associated with milder symptoms.  Neovessels can generate and diminish rather quickly and could therefore be highly responsive to change in condition. 					
Infrapatellar bursitis sign w13	Either denoted as thickened bursa (yes/no) or appearing with doppler as rated by sonographers (1-4 nominal scale).	In our previous cohort at 2-year follow-up, almost all participar still experiencing knee-pain also had Flaviis grade 4 (associat infrapatellar bursitis) at baseline, whilst participants classified grade 1 (normal) were less likely to report pain at follow-up.  Thus, the sole finding of bursitis signs in the infrapatellar burs will be tested as mediator.					

Outcome					
Knee-related Function in Sport/Rec w22	Self-reported on KOOS-child 'Sport/play' subscale, which measure how painful certain movements related to sports- and recreational activities are perceived on 7 items ranging from 'no pain' to 'extreme pain' on a 1-5 Likert scale, normalized to a 0-100 score.	Primary outcome outcome collected at 22 weeks.			

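### The printed confounder list for the mediation analysis does not name baseline KOOS-child Sport/play, so under two conditions a mediator with no effect on the outcome can show an indirect effect

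*Combined protocol and SAP*

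**What the plan says.** The section on assumptions for causal mediation analysis recognises that the mediator-outcome path can be confounded. Its remedy is "To address assumption 2, we will include pre-treatment confounders based on available evidence and clinical expertise", followed by "This includes potential covariates/moderator variables outline (table 12) and baseline levels of the mediator-variables".

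Table 12 prints eight potential moderators/covariates: growth velocity, growth timing, fear of movement (tagged week 13), pain intensity, pain frequency (KOOS-child Pain item P1), treatment expectations, tibial tubercle maturation and Flaviis severity. It prints ten potential mediators. Baseline KOOS-child Sport/play is in neither list. It is also absent from the moderators in Table 1, from the primary model and its example code, and from the statistical approach to mediation analysis.

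For the outcome, Table 12 gives the Sport/play score, with the note "Primary outcome outcome collected at 22 weeks". The primary analysis instead uses change scores, which "from baseline to month 5 will be calculated for all participants". The baseline score is therefore held for this purpose, and Table 11 schedules it at month 0.

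On model size, the section on number of predictors says "we calculated the potential number of predictors as 16" and "we have included 15 predictors (8 mediators and 7 potential covariates/moderators".

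**The concern.** The baseline value of an outcome is usually among its strongest predictors. Here it may also predict the mediators. Table 12 describes Sport/play as a rating of how painful sport movements are, and pain during maximal knee loading is one of the mediators. Appendix 1 reports that a loading-pain test was associated with current Sport/play and responsive to changes in it. If baseline Sport/play drives both a later mediator and the month-5 outcome and is left out, the mediator's coefficient in the outcome model absorbs part of the baseline effect. Multiplied by the treatment effect on the mediator, this becomes an indirect effect that does not exist.

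Therapeutic alliance is the most exposed mediator. Table 11 collects it only at month 3, so it has no baseline level to adjust for.

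The plan will report each mediator's percentage contribution to the total effect and presents this as a guide to optimising the treatment. A wrong attribution could credit or discredit the wrong component.

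**Working it through.** **The plan's own figures.** The sample-size section uses a 9-point difference, SD 16, one-sided 5% and 90% power. An exact one-sided t-test gives 54.82 per group (stated: 54.8), and 55 / 0.85 = 64.7, so 65 per group and 130 in total, as stated. These figures are not in dispute; they supply the 9-point and 16-point scale below.

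**Set-up.** One mediator that treatment changes but that has no effect on the outcome. All variables are standardised and oriented so that higher is better. The outcome model adjusts for arm, the mediator's own baseline and baseline pain, standing in for the planned adjustment. Assumed inputs, since the documents give no correlations:

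- treatment shifts the mediator by a = 0.5 SD;
- carry-over from baseline to later mediator, s = 0.4;
- baseline Sport/play predicts the later mediator beyond its own baseline by g = 0 to 0.3 SD;
- correlation of baseline Sport/play with the baseline mediator r_m = 0.3 to 0.5, with baseline pain r_p = 0.3 to 0.7, and with month-5 Sport/play r_y = 0.3 to 0.7;
- SD 16 for the score. The plan's 16 is the SD of improvement; at r_y = 0.5 the two agree, because 16 x sqrt(2 x (1 - 0.5)) = 16.

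**Formulas.**

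- Variance of baseline Sport/play left after adjustment: v = 1 / [1 + r_m²/(1 - r_m²) + r_p²/(1 - r_p²)].
- Variance of the mediator left after adjustment: w = g²v + 1 - (s² + g² + 2·s·g·r_m).
- False mediator coefficient: g·r_y·v/w for the score, and g·(r_y - 1)·v/w for the change.
- False indirect effect in points: a x coefficient x 16.

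**One case in full** (g = 0.3, r_m = 0.3, r_p = 0.5, r_y = 0.5). v = 1 / (1 + 0.0989 + 0.3333) = 0.698. w = 0.09 x 0.698 + 1 - (0.16 + 0.09 + 0.072) = 0.741. The coefficient is 0.3 x 0.5 x 0.698 / 0.741 = 0.141. The indirect effect is 0.5 x 0.141 x 16 = 1.13 points. For the change score, r_y - 1 = -0.5 gives -1.13.

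| g | r_m | r_p | r_y | Score, points | Change, points |
|---|---|---|---|---|---|
| 0 | 0.3 | 0.5 | 0.5 | 0 | 0 |
| 0.1 | 0.3 | 0.5 | 0.3 | +0.21 | -0.48 |
| 0.2 | 0.3 | 0.5 | 0.5 | +0.72 | -0.72 |
| 0.3 | 0.3 | 0.5 | 0.5 | +1.13 | -1.13 |
| 0.3 | 0.3 | 0.3 | 0.5 | +1.33 | -1.33 |
| 0.3 | 0.3 | 0.3 | 0.7 | +1.86 | -0.80 |

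As shares of 9 points, the non-zero score results run from 0.21/9 = 2% to 1.86/9 = 21%, and the change results from 0.48/9 = 5% to 1.33/9 = 15%. A simulation of 1,000,000 records per scenario agrees to within 0.02 points. With a = 0 the false indirect effect is 0. With baseline Sport/play in the model it is 0.00 in every scenario.

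**At n = 130.** With treatment moving the mediator by 0.8 SD, g of 0.2 to 0.3, and both paths tested at two-sided 5% (4,000 replicates), the false-positive rate is 8-29% for the score and 15-30% for the change. It is about 5% with baseline Sport/play included. With g = 0 it is about 5% either way.

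**Predictor count.** 8 + 7 = 15, and adding one gives 16, the stated maximum. Table 12 as printed gives 10 + 8 = 18. The section also quotes "alpha level of 5% (t = 1.658, Df = 109", but 16 predictors with 130 participants leave 130 - 16 - 1 = 113 degrees of freedom; 109 would correspond to 20 predictors. No effect size is given, so the limit of 16 cannot be rebuilt.

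**The case against.** The strongest reply is that the plan already adjusts for close relatives of baseline Sport/play. Baseline pain intensity, pain frequency and the mediators' own baseline levels carry much of the same information. If they carry all that matters for the later mediator, nothing is lost. For example, let baseline Sport/play correlate 0.5 with the baseline mediator, and let that correlate 0.6 with the later mediator. The marginal correlation is then 0.5 x 0.6 = 0.30, yet the bias is zero once the baseline mediator is in the model. This stands, and it makes the bias conditional. It also rules out a simpler sum that a reader might try: ignoring the planned adjustment, marginal correlations of 0.2 to 0.4 with r_y = 0.5 give 0.5 x 0.5 x 0.2 x 16 = 0.8 to 0.5 x 0.5 x 0.4 x 16 = 1.6 points, but that is not the planned model.

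Three other stronger readings are tempting and not supported:

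- That the predictor count shuts baseline Sport/play out. By the plan's own figures one place is free. The count also omits the baseline mediator levels that the plan says it includes, so absence from it does not show exclusion from the model.
- That the causal graph lacks the variable. The graph is not visible here, and the sentence introducing the list is not strictly exhaustive.
- That the no-confounding assumption is shown to fail. No correlation between baseline Sport/play and any later mediator is given, and nothing shows that baseline function drives therapeutic alliance.

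The plan also treats the mediation analysis as secondary, conditional on superiority of arm A, and to be read with caution. That limits the consequence. However, the caution is about power and precision and does not address bias.

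**Conclusion.** The omission from the printed list holds. A false indirect effect may follow if treatment moves the mediator and baseline Sport/play predicts the later mediator beyond its own baseline and the listed covariates. Under the assumed correlations and one mediator at a time, the size is 0 when either condition fails, otherwise about +0.2 to +1.9 points on the week-22 score or -0.5 to -1.3 points on the change score. The signs assume that treatment shifts the mediator in the direction that goes with better baseline function; otherwise they reverse. Using the change score does not remove the bias.

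The plan fits several mediators jointly, so these figures show the order of magnitude and cannot be added up or read off mediator by mediator. For therapeutic alliance the second condition is easier to meet, because only the listed covariates stand between it and baseline function. The primary result is unaffected.

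**What to change.** Name baseline KOOS-child Sport/play as a covariate in every mediator model and in the outcome model. List it in Table 12, and in the directed acyclic graph if it is not already there. State whether the mediation outcome is the week-22 score or the change; once the baseline is in a linear outcome model, both give the same mediator coefficients.

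Reconcile the predictor count at the same time: 8 + 7 in the text against 10 mediators and 8 covariates in Table 12, whether baseline mediator levels are counted, and the 109 degrees of freedom.

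The cost is a wording change in the analysis plan and one model term on data already collected. On the plan's own count this makes 16 predictors, equal to its stated maximum. It should be done before the unblinded analysis.
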